# 14 Appendix 2: Liver event definitions and follow-up requirements

Confidential

	Definition/ threshold	
Adverse event of special interest		
Laboratory values	ALT or AST > 3 x ULN	
	$ALP > 2 \times ULN$	
	TBL > 1.5 x ULN	
Medically significant event (SAE)		
Laboratory values	ALT or AST > 5 x ULN (with or without TBL > 2 x ULN [mainly conjugated fraction])	
	ALP > 5 x ULN (with or without TBL > 2 x ULN [mainly conjugated fraction])	
	TBL > 3 x ULN	
	Potential Hy's Law cases (defined as ALT/AST > 3 x ULN and TBL > 2 x ULN [mainly conjugated fraction] without notable increase in ALP to > 2 x ULN)	
Adverse events	Any clinical event of jaundice (or equivalent term)	
	ALT or AST > 3 x ULN accompanied by general malaise, fatigue, abdominal pain, nausea, or vomiting, or rash with eosinophilia	
	Any event that links to a preferred term (PT) in the MedDRA dictionary falling under the SMQ sub-module "Drug-related hepatic disorders – severe events only"* or any "Hy's law case" PT	

\* These events cover the following: hepatic failure, fibrosis and cirrhosis, and other liver damage-related conditions; the non-infectious hepatitis; the benign, malignant and unspecified liver neoplasms

Table 14-2     Liver Event Follow Up Requirements					
Criteria	Event type	Actions required	Follow-up monitoring		
Potential Hy's Law case a	Medically significant	Discontinue the study drug immediately Hospitalize, if clinically appropriate Report to Novartis as an SAE Establish causality	ALT, AST, TBL, Alb, PT, ALP and γGT until resolution c (frequency at investigator discretion)		
ALT or AST		,			
> 8 x ULN	Medically significant	Repeat LFT within 48 hours If elevation persists, discontinue the study drug immediately Hospitalize if clinically appropriate Report to Novartis as an SAE Establish causality	ALT, AST, TBL, Alb, PT, ALP and γGT until resolution c (frequency at investigator discretion)		
> 5 to ≤ 8 x ULN	Medically significant	Repeat LFT within 48 hours If elevation persists for more than 2 weeks , discontinue the study drug Report to Novartis as an SAE Establish causality	ALT, AST, TBL, Alb, PT, ALP and γGT until resolution c (frequency at investigator discretion)		

#### Tabl т. T 11 n тт •

Criteria	Event type	Actions required	Follow-up monitoring
		Repeat LFT once or twice in the week If elevation persists, establish causality	
≤ 2 x UL N (patient is asymptomatic)	N/A	Repeat LFT at next visit	
TBL (isolated)			
> 3 x ULN	Medically significant	Repeat LFT within 48 hours If elevation persists, discontinue the study drug immediately Hospitalize if clinically appropriate Report to Novartis as an SAE Establish causality	ALT, AST, TBL, Alb, PT, ALP and γGT until resolution c (frequency at investigator discretion) Test for hemolysis (e.g., reticulocytes, hemoglobin, unconjugated [indirect] bilirubin)
> 1.5 to ≤ 3 x ULN (patient is asymptomatic)	AESI	Central laboratory to report to Novartis Repeat LFT once or twice in the week If elevation persists, establish causality	investigator discretion Monitor LFT within 1 to 4 weeks or at next visit
≤ 1.5 x ULN (patient is asymptomatic)	N/A	Repeat LFT at next visit	
Preferred terms			
Jaundice	Medically significant	Discontinue the study drug immediately Hospitalize the patient Report to Novartis as an SAE Establish causality	ALT, AST, TBL, Alb, PT, ALP and γGT until resolution c (frequency at investigator discretion)
"Drug-related hepatic disorders - severe events only" SMQ AE	Medically significant	Discontinue the study drug hospitalization if clinically appropriate Report to Novartis as an SAE Establish causality	Investigator discretion

a Elevated ALT/AST > 3 x ULN and TBL > 2 x ULN but with no notable increase in ALP to > 2 x ULN

b General malaise, fatigue, abdominal pain, nausea, or vomiting, rash with eosinophilia

c Resolution is defined as an outcome of one of the following: return to baseline values, stable values at three subsequent monitoring visits at least 2 weeks apart, remain at elevated level after a maximum of 6 months, liver transplantation, and death.

# 15 Appendix 3: Study Assessments and Questionnaires

## 15.1 Six Minute Walk Test

#### > Key Points

- The 6MWT must be performed once or else twice to account for a learning curve.
- \*Note: consistency in administering the test is imperative. If the test was performed once at baseline it should be performed once at all subsequent visits, if performed twice at baseline it should be performed twice at all subsequent visits.
- If the two tests are performed on the same day, at least 30 minutes rest should be allowed between tests.

\*Note: debilitated individuals may require tests to be performed on separate days, preferably less than one week apart.

- Results of both tests are recorded with the best result used to determine functionality.
- A health professional trained in CPR with the ability to run the test must be present.

#### >Required Equipment

- Walking Track or Area
  - The walking track or area must be the same for all tests for a patient
  - The track may be a continuous track (oval or rectangular) or a point-to-point area (stop- turn around-go back).
  - The track or area should be flat with no blind turns, traffic or obstacles.
  - The minimum walking length of 25m (82 feet) should be marked in meter (feet) increments.

\*Note: If you do not have access to a 25m track, make sure you use the same point-to- point area for all tests (be aware that the distance walked may be less due to the patient having to slow down and turn more often in the six minutes).

- Stethoscope, vital sign equipment, pulse oximeter
- Stop watch
- Portable oxygen delivery system
- Chairs in position for the patient to rest
- Dyspnea scale

>Before the 6MWT

• Ensure that you have already obtained a medical history for the patient and have

taken into account any precautions or contraindications to exercise testing.

• Instruct the patient to dress comfortably, wear appropriate footwear and to avoid eating for at least two hours before the test (where possible or appropriate).

Confidential

- Any prescribed inhaled bronchodilator medication should be taken within one hour of testing or when the patient arrives for testing.
- The patient should rest for at least 15 minutes before beginning the test.
- A comfortable ambient temperature and humidity should be maintained for all tests.
- Record:
  - Blood pressure
  - Heart rate
  - Oxygen saturation
  - Dyspnea score

\* Note: Show the patient the dyspnea scale (e.g., Borg scale) and give consistent instructions on how to obtain a score.

#### • Instructions to the Patient

\*Note: Instructions must be consistent.

(Read out loud the instructions to the patient.)

- Describe the walking track or area to the patient.
- Explain the objective of the test.
- Provide instructions on what to do and what not to do during the test.
- Emphasize reporting any untoward effects.
- Sample instructions:

"You are now going to do a six-minute walking test. The object of this test is to walk as quickly as you can for six minutes around the track (or up and down the corridor etc... depending on your track set up) so that you cover as much ground as possible. You may slow down if necessary. If you stop, I want you to continue to walk again as soon as possible. You will be kept informed of the time and you will be encouraged to do your best. Your goal is to walk as far as possible in six minutes. Please do not talk during the test unless you have a problem or if I ask you a question. You must let me know if you have any chest pain or dizziness. When the six minutes is up I will ask you to stop where you are. Do you have any questions?"

> **Begin the Test** by instructing the patient to start walking and start the stop watch.

#### > During the Test

- Monitor the patient for untoward signs and symptoms.
- Use standard encouragements during the test. Example:
  - At minute one: "Five minutes remaining. Do your best!"
  - At minute two: "Four minutes remaining. You're doing well- keep it up!
  - At minute three: "Half way point. Three minutes remaining!"
  - At minute four: "Two minutes remaining. You're doing well- keep it up!
  - At minute five: "One minute remaining. Do your best!"

#### > At the End of the 6MWT

• Put a marker on the distance walked.

• Have the patient sit down or if the patient prefers, allow to the patient to stand. \*Note: The measurements taken before and after the test should be taken with the patient in the same position.

Confidential

- Immediately record oxygen saturation (SpO2)%, heart rate, and dyspnea rating on the recording sheet.
- Measure the excess distance with a tape measure and add up the total distance.
- The patient should remain in a clinical area for at least 15 minutes following an uncomplicated test.

>Clinical Notes

Normally the clinician does not walk with the patient during the test to avoid the problem of setting the walking pace. The pulse oximeter should be applied immediately if the patient chooses to rest and at completion of the six-minute walking period. Any delay may result in readings being recorded that are not representative of maximum exercise response.

In some instances, the clinician may choose to walk with the patient for the entire test (e.g., if continuous oximetry is desired). If this is the case the clinician should try to walk slightly behind the patient to avoid setting the walking pace. Alternatively, if the oximeter is small and lightweight, it may be attached to the patient and checked throughout the test without interfering with walking pace.

> If the Patient Stops During the Six Minutes

- Allow the patient to sit in a chair if they wish.
- Measure the SpO2% and heart rate.
- Ask the patient why they stopped.
- Record the time the patient stopped (but keep the stop watch running).
- Encourage the patient to begin walking as soon as he/she is feeling better and offer encouragement every 15 seconds if necessary.
- Monitor the patient for untoward signs and symptoms.

>Stop the Test in the Event of Any of the Following

- Chest pain suspicious for angina.
- Evolving mental confusion or lack of coordination.
- Evolving light-headedness.
- Intolerable dyspnea.
- Leg cramps or extreme leg muscle fatigue.
- Persistent SpO2 < 85%.
- Any other clinically warranted reason.

> Predicted Normal Values for the 6MWT

The following predictive equation uses the reference values determined from a study

that performed two 6MWTs and recorded the best result: (For more details see Troosters T, Gosselink R, Decramer M. Six minute walk distance in healthy elderly subjects. Eur Respir J. 1999;14: 270-274).

Confidential

- Predicted six-minute walk distance in healthy elderly =  $631 \pm 93$  meters
- Predictive equation: 6MWDpred = 218 + (5.14 x heightcm 5.32 x age) 1.80 x weightkg + 51.31 x gender
   Note: Gender is factored into the equation by male = 1, female = 0.

> 6MWT as an Outcome Measure

The change in the distance walked in the 6MWT can be used to evaluate the efficacy of an exercise training program or to trace the natural history of change in exercise capacity over time.

The minimum clinically important difference (i.e., improvement) in the distance walked in a 6MWT has been estimated as 54 meters (with 95% confidence limits of 37 to 71 meters) (For further details, see Redelmeier, 1997).

However, this improvement in 6MWT distance may not occur in patients who walk a very short distance in their 6MWT before pulmonary rehabilitation. For these patients, it may be more reasonable to evaluate efficacy based on the percent change rather than a change in a set number of meters. However, the actual percent change that equates to a clinical improvement has not yet been established - further research is required.

All Rights Reserved © [name]

# **U** NOVARTIS

	5.4.2	Secondary anlysis	2
	Rule of	exclusion criteria of analysis sets	2
	Adverse	e event of special interest	2
	Target of	lose of cardiovascular medication	

	Document Histor	y – Changes	compared	to previous	version of SAP	module 3.
--	------------------------	-------------	----------	-------------	----------------	-----------

Version	Date	Changes
Final 1.0	29-APR-2016	Initial draft
Amendment 1	27-Jul-2017	As per Protocol few amendment sections got updated
		Section 2.11 6MWT analysis updated; few sites won't be performing 6MWT twice
		Section 2.2 Added definition of enrolled set
		Section 2.4.1 analysis regarding compliance
		Section 5.5 Rule of exclusion criteria of analysis sets
		Section 5.6 Adverse event of special interest
		Section 5.7 Target dose of cardiovascular medication
Addendum 1	24-Apr-2018	Section 2.11 6 MWT analysis change, Observations with total distance walked >1000 m will be excluded from the analysis.
		Section 2.8.3 Laboratory data, handling unit coversion for
		creatinine and unc acid programmatically.

List of abbreviations

ACE	angiotensin converting enzyme
ACEI(s)	angiotensin converting enzyme inhibitor(s)
AE	Adverse event
ALT	alanine aminotransferase
ANP	atrial natriuretic peptide
APP	aminopeptidase P
ARB(s)	angiotensin receptor blocker(s)
ARNi(s)	Angiotensin Receptor Neprilysin Inhibitor(s)
AST	aspartate aminotransferase
AT1	angiotensin type 1bid twice a day
bid	bis in diem/twice a day
BP	blood pressure
CHF	chronic heart failure
CSR	Clinical Study report
СРО	Country Pharma Organization
CRF	Case Report/Record Form (paper or electronic)
CSR	Clinical Study Report
CRO	Contract Research Organization
CV	cardiovascular
DBP	diastolic blood pressure
DMC	Data Monitoring Committee
DS&E	Drug Safety & Epidemiology
EC(s)	Ethics Committee(s)
ECG	Electrocardiogram
EDC	Electronic Data Capture
eGFR	estimated glomerular filtration rate
EOS	end of study
FAS	Full Analysis Set
HF	Hearth Failure
ICH	International Conference on Harmonization of Technical Requirements for Registration of Pharmaceuticals for Human Use
IEC	Independent Ethics Committee
IRB	Institutional Review Board
IRT	Interactive Randomization TechnologyLCZ696 Novartis compound code
LVEF	left ventricular ejection fraction
MDRD	Modification of Diet in Renal Disease
MedDRA	Medical Dictionary for Drug Regulatory Affairs
mg	milligram
NP(s)	natriuretic peptide(s)
NYHA	New York Heart Association
o.d.	once a day
РК	Pharmacokinetics
PPS	Per-Protocol Set
PRO	Patient-reported Outcomes
p.o.	oral

Novartis	For business use only	Page 6
SAP		PARASAIL / LCZ696BCA02
QoL	Quality of Life	
SAE	serious adverse event	
SAP	Statistical Analysis Plan	
SBP	systolic blood pressure	
SOC	System Organ Class	
TFLs	Tables, Figures, Listings	
ULN	upper limit of normal	
WHO	World Health Organization	

1 Introduction

The main purpose of this Statistical Analysis Plan (SAP) is to provide summary of the statistical methodology that will be used for this study; this includes a detailed description of data summaries. Analysis plans in this document refer to the related statistical analysis sections in clinical study reports.

This SAP module describes the statistical analysis according to Section 9 of the study protocol along with specifications or deviations planned.

Data will be analyzed according to the data analysis section 9 of the study protocol which will be available in Appendix 16.1.1 of the CSR. Important information is given in the following sections 2.7 (Efficacy evaluation), 2.8 (Safety evaluation), 2.14 (Interim analysis) and 3 (power and sample size considerations).

1.1 Study design

This will be a multi-center, open label, prospective post-approval (phase IV) study. Patients with HFrEF that are eligible to be treated with LCZ696 as per the product monograph will be enrolled in the study. The study patients will be enrolled at Canadian community cardiologists and IM specialists that treat patients with HFrEF. Follow up will be for 12 months with assessments at baseline, week 2, week 4, month 3 (optional), month 6 and month 12. The primary endpoint will be assessed after 6 months of follow-up.

Treatment with ACEIs will be discontinued for 36 hours and then replaced with LCZ696 at 24 mg sacubitril / 26 mg valsartan bid. NO washout period is needed for patients previously treated on ARBs. The dose of LCZ696 will be increased to 49 mg sacubitril / 51 mg valsartan bid within 2-4 weeks of enrolment and to 97 mg sacubitril / 103 mg valsartan bid within 2-4 weeks from the first up titration to 49 mg sacubitril / 51 mg valsartan bid as tolerated by the patient and in accordance to the product monograph (Figure 1-1). Down titration of LCZ696 from the higher doses may be considered, as per the product monograph for patients that experience tolerability issues including, but not limited to, symptomatic hypotension or hyperkalemia.

Figure 1-1 Study design

* Titration scheme in the study protocol will reflect approved Canadian product monograph

* LCZ696 50 mg bid is the equivalent of 24 mg sacubitril / 26 mg valsartan bid

* LCZ696 100 mg bid is the equivalent of 49 mg sacubitril / 51 mg valsartan bid

* LCZ696 200 mg bid is the equivalent of 97 mg sacubitril / 103 mg valsartan bid

1.2 Study objectives and endpoints

1.2.1 Primary objective

The primary objective of this study is to describe the tolerability of LCZ696 at 97 mg sacubitril / 103 mg valsartan bid, after 6 months of treatment in patients with HFrEF.

1.2.2 Secondary objectives

In patients with HFrEF:

- To describe the tolerability of LCZ696 at 97 mg sacubitril / 103 mg valsartan bid, after 12 months of treatment.
- To evaluate the impact of the titration scheme on the tolerability of patients maintained on LCZ696 97 mg sacubitril / 103 mg valsartan bid at 6 and 12 months
- To describe the impact of LCZ696 on functional exercise capacity, as measured by the Six Minute Walk Test, at 6 and 12 months.
- To describe the time of up-titration for each dose (24 mg sacubitril / 26 mg valsartan bid / 49 mg sacubitril / 51 mg valsartan bid) of LCZ696.
- To describe the adherence to guideline recommended dosing of beta-blockers and MRAs at 6 and 12 months of treatment with LCZ696.
- To evaluate the overall safety profile of LCZ696 during 12 months of treatment.

2 Statistical methods

The data analysis for the current study will be primarily descriptive. Descriptive statistics will be produced for all study variables. The descriptive statistics will include mean, median, SD and 95% confidence interval of the mean for continuous scale variables and frequency distributions with 95% confidence intervals around the estimate of proportions will be reported for categorical scale variables.

For categorical data, percentages will be rounded up to 1 decimal place. For continuous data, mean, median and quartiles will be rounded up to 1 additional decimal place compared to the original data. Standard deviation will be rounded up to 2 additional decimal places. Minimum and maximum will be displayed with the same accuracy as in the original data. Wherever changes from baseline will be used, change will be calculated as "post-baseline value – baseline value". The number of decimal places for the "change from baseline" variables will be the same as for the original measurement.

2.1 Data analysis general information

Statistical Analysis System (SAS) version 9.4 or higher will be used to perform all the statistical analyses in the report.

The data analysis for the current study will be primarily descriptive. 95% confidence intervals will be calculated for the estimate of proportions in order to assess precision and make inferences to the target population.

Safety will be assessed with the incidence of treatment emergent adverse events.

2.2 Analysis sets

The following analysis sets will be used for statistical analysis:

- Screened set (SCR) Screened set will be comprised of all patients given informed consent.
- Enrolled set (ENR) Patients who have met the eligibility criteria or has taken at least one dose of study medication.
- Full analysis set (FAS) The Full Analysis Set (FAS) will be comprised of all patients that have received at least one dose of LCZ696. The primary analysis will be based on the FAS.
- Per protocol set (PPS) The Per-Protocol Set will be comprised of the patients that complete the 6 month and 12 month follow up assessments depending on the time period analyzed. The analyses will be repeated for the PPS if there is a more than 10% difference between the FAS and PPS samples.
- Safety Set (SAF)- Safety set includes all the patients in FAS.

All analyses will be performed in both the FAS and PPS, unless otherwise specified. All Safety analysis will be performed on Safety Set.

2.2.1 Subgroup of interest

NYHA class will be used as subgroup of interest. Patient reported outcome will be provided by NYHA class II and NYHA class III.

2.3 Patient disposition, demographics and other baseline characteristics

Descriptive statistics will be reported for patient demographics and baseline characteristics. This will include the mean, median, standard deviation, minimum and maximum for continuous variables. Frequency distributions will be reported for categorical variables.

2.3.1 Patient disposition

The number and percentage of enrolled, completed, and discontinued in the study and reason for the discontinuation and screen failure will be provided. For patient who was screened more than once, the information from the last screen will be used in the summary. Data will be summarized using FAS.

The number and percentage of the patients with protocol deviations as well as the criteria leading to exclusion from analysis sets will be presented in separate table for the FAS.

2.3.2 Background and demographic characteristics

Descriptive statistics will be provided for patient demographics and baseline characteristics.

The following demographic and baseline parameters will be summarized at the visit 1 (day 1):

• Demographics

- Age (Years)
- o Gender
- Race (Caucasian, Black, Asian, Native American, Pacific Islander, Unknown, Other)
- Ethnicity (Hispanic or Latino, east Asian, Southeast Asian, South Asian, West Asian, Russian, Mixed Ethnicity, Not reported, Unknown, Other)
- o Height (Cm)
- Weight (kg)
- Body Mass Index (BMI) (kg/m2)
- Smoking history
- Alcohol use history

• Medical History

Any condition entered on the relevant medical history / current medical conditions will be coded using the MedDRA dictionary. Medical history includes cardiovascular disease history in this study, which are collected prior to informed consent signature.

The number and percentage of subjects with each medical condition will be provided by system of organ class for the FAS.

The above medical conditions will also be listed.

• Heart Failure History

Novartis	For business use only	Page 11
SAP		PARASAIL / LCZ696BCA02

Heart failure history will be summarized by number and percent for following categories.

- Primary HF etiology (Ischemic /Non ischemic)
 - If Non ischemic:
 - Hypertensive (Yes/No)
 - Diabetic (Yes/No)
 - Alcoholic (Yes/No)
 - Viral cardiomyopathy (Yes/No)
 - Infectious cardiomyopathy (Yes/No)
 - Peripartum (Yes/No)
 - Drug induced (Yes/No)
 - Hypertrophic cardiomyopathy (Yes/No)
 - Idiopathic (yes/No)
 - Unknown (Yes/No)
- Prior heart failure hospitalization(yes/no)
- Number of hospitalization in the last 12 months
- Ejection Fraction (%) in last 12 months
- NYHA class at enrollement
- Timing since last ejection fraction (months)

The above demographic and heart failure history will also be listed based on FAS.

2.4 Treatments (study treatment, rescue medication, concomitant therapies, compliance)

2.4.1 Study treatment / compliance

The duration of the study treatment exposure will be summarized (n, mean, standard deviation, minimum, median, and maximum). Descriptive statistics will be based on SAF.

The exposure duration categories are defined for each phase as:

- Day 1
- >= 2 Weeks
- >= 4 Weeks
- >= 12 Weeks
- >= 24 Weeks
- >= 52 Weeks (12 Months)

Treatment duration (days) = (date of last dose of LCZ696 - date of first dose of LCZ696) + 1

Compliance with treatment will be defined as the percentage of doses taken by the patient and

will be calculated using the following formula:

Compliance (%) = 100 x (total number of capsules dispensed – total number of capsules

returned) / total number of capsules dispensed. In addition listing for the total number of missed doses by each patient will be provided.

This information will be used as a measure of the number of tablets taken between study visits for compliance.

The durations on each dose level, time from the first dose intake to the final top dose will also be summarized.

2.4.2 **Prior**, concomitant and post therapies

The concomitant medication information will be summarized based on the SAF.

Concomitant medications and significant non-drug therapies, prior to and after the study treatment will be summarized by therapeutic class, preferred term according to the WHO-DRL dictionary. Also, cardiovascular concomitant medication will be summarized separately.

As before, concomitant medication will be identified based on recorded or imputed start and end dates of medication taking. The rules for imputing incomplete (start and end) dates are described in Section 5.1.3.

The proportion of patients on guideline recommended dose of beta-blockers and MRAs at baseline ,6 and 12 months will also be summarized.

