#### 5.5.3 Handling of study treatment

# 5.5.3.1 Handling of investigational treatment

Investigational treatment must be received by a designated person at the study site, handled and stored safely and properly, and kept in a secured location to which only the investigator and designees have access. Upon receipt, all investigational treatment should be stored according to the instructions specified on the labels. Clinical supplies are to be dispensed only in accordance with the protocol.

Medication labels will be in the local language and comply with the legal requirements of each country. They will include storage conditions for the investigational treatment but no information about the patient except for the study specific Subject Number.

The investigator must maintain an accurate record of the shipment and dispensing of investigational treatment in a drug accountability log. Monitoring of drug accountability will be performed by the field monitor during site visits and at the completion of the trial. Patients will be asked to return all unused investigational treatment and packaging at each study visit and at the end of the study or at the time of discontinuation of investigational treatment.

At the conclusion of the study, and as appropriate during the course of the study, the investigator will return all unused investigational treatment, packaging, drug labels, and a

copy of the completed drug accountability log to the Novartis monitor or to the Novartis address provided in the investigator folder at each site.

Confidential

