# 6.3 **Treatment exposure and compliance**

All patients will be treated with LCZ696 at 24 mg sacubitril / 26 mg valsartan, 49 mg sacubitril / 51 mg valsartan and 97 mg sacubitril / 103 mg valsartan bid. The dose prescribed for each patient during the up-titration will be recorded in the CRF. All patients will be instructed to return all unused medication at each visit. The site staff will record the number of tablets returned versus those dispensed at the previous visit, and this information will be used to calculate the number of doses missed. In addition, at each follow up visit, the patients will

be asked how many times they did not take any of their prescriptions for heart disease as instructed by their physicians.

Confidential

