#### 9.3 **Treatments**

Novartis

All LCZ696 doses administered to the patients will be recorded in the CRF. The number of tablets dispensed at the previous visit minus the number of tablets returned by patients at each study visits, will be used as a measure of the number of tablets taken between study visits.

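### The SAP compliance formula divides by tablets dispensed rather than prescribed, so tablets returned for legitimate reasons count as non-compliance

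*SAP*

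**What the plan says.** SAP 2.4.1 gives the concept first: "Compliance with treatment will be defined as the percentage of doses taken by the patient and" then the calculation, which begins "Compliance (%) = 100 x (total number of capsules dispensed – total number of capsules" and ends "returned) / total number of capsules dispensed". The same section adds: "In addition listing for the total number of missed doses by each patient will be provided". It does not say how a missed dose is derived. (It writes capsules in the formula and tablets just afterwards; the product is a tablet.)

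Protocol 6.3 requires that "All patients will be instructed to return all unused medication at each visit", and Protocol 5.5.3.1 repeats it: "Patients will be asked to return all unused investigational treatment and packaging at each study visit". Under 6.3, staff record tablets returned against tablets dispensed, and "this information will be used to calculate the number of doses missed". Protocol 9.3 uses the pill count more narrowly: "The number of tablets dispensed at the previous visit minus the number of tablets returned by patients at each study visits" measures tablets taken between visits. It specifies no denominator.

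No section of either document brings the number of tablets prescribed into the compliance calculation, or removes surplus or superseded-strength tablets from it.

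**The concern.** Percentage of doses taken needs the doses that should have been taken as its denominator. Tablets dispensed equals that number only when supply exactly matches need, and this design makes surplus likely:

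- Three strengths are supplied, and each titration step is timed at 2-4 weeks by tolerability and physician judgement (Protocol 5.5.2, 5.5.5).
- Dose reductions and interruptions are permitted (Protocol 5.5.6).
- Visits have a 7-day window (Protocol 6), so some spare supply is foreseeable.
- All unused tablets are to come back at each visit.

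The reported percentage would then mix adherence with how much was handed out and when the dose changed. A reader of the study report would take a score below 100% to mean omitted doses, and the per-patient listing might name missed doses for patients who missed none.

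**Working it through.** The plan states no compliance figure, so there is nothing to reproduce.

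**Algebra.** Let D = tablets dispensed, R = returned, P = prescribed. The SAP score is 100 × (D − R)/D. For a patient who takes every prescribed dose and returns the rest, D − R = P, so the score is 100 × P/D. This is below 100% whenever R > 0. With P as denominator the same patient scores 100 × P/P = 100%.

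**Inputs.** Twice-daily dosing is in the documents. One tablet per dose (2 per day) is an assumption, as is every supply quantity below. Over 52 weeks P = 2 × 364 = 728.

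**Whole study, fully adherent patient**

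| Assumed supply | D | R | SAP score | Score with P as denominator |
|---|---|---|---|---|
| Supply equals need | 728 | 0 | 100% | 100% |
| Two 28-day supplies (56 tablets each), each superseded after 14 days | 56 + 56 + 2 × (364 − 28) = 784 | 28 + 28 = 56 | 728/784 = 92.9% | 100% |
| As above, plus two 7-day spare supplies (14 tablets each) | 784 + 28 = 812 | 56 + 28 = 84 | 728/812 = 89.7% | 100% |

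If a missed dose is simply a tablet returned, the last patient is listed with 84 missed doses and missed none.

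**Single intervals, fully adherent patient**

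- 2 weeks (P = 28): 7 days' surplus gives 28/42 = 66.7%; 14 days' gives 28/56 = 50.0%.
- 4 weeks (P = 56): 56/70 = 80.0% and 56/84 = 66.7%.
- Week 4 to week 24 (P = 280): 280/294 = 95.2%, 280/308 = 90.9%, and 280/336 = 83.3% with 28 days' surplus.

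**Interruption.** Suppose 56 tablets for 4 weeks and a 7-day interruption directed by the investigator. The patient takes 42 and returns 14. The SAP gives 42/56 = 75.0%. A prescribed denominator gives 42/42 = 100% only if the interrupted days are removed from it.

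**Direction across titration patterns.** Two supply assumptions give opposite answers.

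- Each lower strength comes as a 28-day supply. A patient moved up after 14 days twice scores 92.9%, as above. One who uses each supply in full before moving up returns nothing and scores 100%. The faster titrator looks worse.
- Supply covers each interval between the dispensing visits that Table 6-1 shows (day 1, week 2, week 4, month 6). A patient moved up at weeks 2 and 4 returns nothing and scores 100%. A patient given 20 weeks of the middle strength at week 4 (280 tablets) and changed at week 8 has taken 56 and returns 224. With supply otherwise matched, the score is 728/(728 + 224) = 76.5%. The slower titrator looks worse.

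The second case also shows that 90-100% illustrates modest surplus and is not a bound.

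**Unreturned tablets.** With 56 dispensed and prescribed, 28 taken and none returned, the SAP score is 56/56 = 100%, and a prescribed denominator also gives 100%. A change of denominator does not cure this.

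**The case against.** The strongest reply is that little depends on this number. The primary endpoint is dose level at 6 months among all patients dosed (SAP 2.5.1). None of the seven secondary endpoints in SAP 2.7.1 is study-drug compliance. No compliance threshold enters the per-protocol set (SAP 2.2, 5.5). Duration on each dose is summarised separately. All of that stands and limits the point to a descriptive summary and a listing.

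The numerator is also sound: it is the protocol's own measure of tablets taken. The missed-dose listing could rest on another source, since Protocol 6.3 also asks patients at each follow-up visit how often they did not take their heart medicines as instructed. The listing problem is therefore conditional.

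Three stronger readings are tempting but unsupported:

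- *Compliance is used to interpret tolerability at the target dose.* Neither document says so. Protocol 5.5.5 gives study validity as a reason to promote compliance with patients, but assigns the score no role in any analysis.
- *Successful titrators will look least compliant.* This depends on quantities dispensed, which are not given; the working shows that the direction can reverse.
- *Adherent patients will score 50-67%.* Those are single short intervals under assumed supplies, whereas the SAP formula is written on totals.

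None of this rescues the denominator: no section corrects it.

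**Conclusion.** The point holds as a defect in a descriptive measure. As written, the formula does not deliver the SAP's own definition: a fully adherent patient who follows the return instruction scores prescribed/dispensed.

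Assuming one tablet per dose and modest surplus, that is about 90-100% over 12 months, and lower within short intervals. The size cannot be fixed from the documents because supply quantities are absent, and the direction of bias across titration patterns cannot be determined. No estimate that answers a primary or secondary endpoint changes. Correction is still worthwhile, because the summary will be read as adherence and the listing may attribute missed doses to individual patients.

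**What to change.** Replace the formula in SAP 2.4.1 with: compliance (%) = 100 × (tablets dispensed − tablets returned) / (tablets prescribed over the same days), per interval and overall, taking prescribed tablets from the Dosage Administration Record CRF. In addition:

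- Pool over strengths, or report by strength where returns are recorded that way; Protocol 6.3 does not say that they are.
- Exclude investigator-directed interruptions from the prescribed count.
- Set compliance to missing for any interval where the return was not made or not counted, and leave that interval out of both parts of the overall figure.
- Flag values above 100%. They can arise from partial returns: with 42 dispensed, 28 prescribed and 7 returned, the score is 35/28 = 125%.
- Derive the missed-dose listing on the same basis, and state that basis in the SAP.

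The cost is SAP wording and a little more programming. Prescribed doses and dose changes are already recorded (Protocol 5.5.5, 5.5.6); whether the record separates investigator-directed interruptions from doses the patient omitted should be confirmed first. The downside is that some intervals become missing. Their number should be reported beside the summary.
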